## **Non-Interventional Study Protocol (PASS)**

### **REDACTED PROTOCOL**

BAF312A2403

Title	Post-Authorization Safety Study for Assessment of Pregnancy Outcomes in Patients Treated with Mayzent (siponimod): An OTIS Observational Pregnancy Surveillance Study
Protocol version identifier	v1.1 (clean)
Date of last version of protocol	15-November-2022
EU PAS register number	Not applicable
Active substance	Siponimod (ATC code: L04AA42 )
Medicinal product	Mayzent, BAF312A
Product reference	Mayzent NDC 0078-0986-15, 0078-0979-12, 0078-0979-50, 0078-0979-92, 0078-0986-93
Procedure number	FDA/PMR 3591-4

Name of marketing authorization holder(s)	Novartis Pharmaceuticals Corporation, [name]
Joint PASS	No
Research question and objectives	
Research question: "Is exposure to siponimod therapy during pregnancy associated with an increased risk of adverse pregnancy or infant outcomes?"
 
The primary objective is to estimate and compare the prevalence of major structural defects in siponimod exposed pregnant women versus 1) disease-matched pregnant women not exposed to siponimod, and 2) healthy pregnant women.
 
Secondary objectives are to estimate and compare the prevalence of selected adverse pregnancy and infant outcomes in siponimod-exposed pregnant women versus 1) disease-matched pregnant women not exposed to siponimod, and 2) healthy pregnant women.
 
The primary outcome of the study is major structural defects, and the secondary outcomes of the study are a pattern of minor structural defects, spontaneous abortion, stillbirth, elective termination, preterm delivery, preeclampsia/eclampsia, small for gestational age infants, and small for age for postnatal growth to one year of age, developmental performance at approximately one year of age, and serious or opportunistic infections in the first year of life.

Country (-ies) of study	United States and Canada (North America)
Author	
[REDACTED] PhD, MPH Principal Investigator [REDACTED]
 
Tel: [REDACTED] Email: [REDACTED]

Property of Novartis

Confidential

May not be used, divulged, published or otherwise disclosed  
without the consent of Novartis

## List of abbreviations

---

AE	Adverse Event
ASQ	Ages and Stages Questionnaire
BMI	Body Mass Index
CDC	Centers for Disease Control and Prevention
CI	Confidence Interval
EC	Ethic Committee
EDSS	Expanded Disability Status Scale
EMA	European Medicines Agency
ENCePP	European Network of Centres for Pharmacoepidemiology and Pharmacovigilance
EU	European Union
FDA	Food & Drug Administration
FPFV	First Patient First Visit
GEE	Generalized Estimating Equations
GMA	Global Medical Affairs
GPP	Good Pharmacoepidemiology Practices
HA	Health Authority
HCP	Health Care Provider
HIPAA	Health Insurance Portability & Accountability Act
HR	Hazard Ratio
ICD-9-CM	The International Classification of Diseases, 9th Revision, Clinical Modification
ICF	Informed Consent Form
ICH	International Conference on Harmonization
IPW	Inverse Probability Weighing
IRB	Institutional Review Board
ISPE	International Society for Pharmacoepidemiology
LMP	Last Menstrual Period
LTFU	Lost-To Follow-Up
LPLV	Last Patient Last Visit
MACDP	Metropolitan Atlanta Congenital Defects Program
MAH	Marketing Authorization Holder

---

MI	Multiple Imputation
MICE	Multivariate Imputation by Chained Equations
MS	Multiple Sclerosis
NCHS	National Center for Health Statistics
NI	Non-Interventional
NIS	Non-Interventional Study
NVS	Novartis
OTIS	Organization of Teratology Information Specialists
PASS	Post-Authorization Safety Study
PMS	Post Marketing Surveillance
PS	Propensity Score
RR	Risk Ratio
SAB	Spontaneous Abortion
SAE	Serious Adverse Event
SAP	Statistical Analysis Plan
SMD	Standardized Mean Differences
SOP	Standard Operating Procedure
SPMS	Secondary Progressive Multiple Sclerosis
STROBE	Strengthening the Reporting of Observational Studies in Epidemiology
US	United States
WHO	World Health Organization

---

## 2 Abstract

### Title

Post-Authorization Safety Study for Assessment of Pregnancy Outcomes in Patients Treated with Mayzent (siponimod): An OTIS Observational Pregnancy Surveillance Study

### Version and date

v1.1 15 November 2022

### Rationale and background

Mayzent (siponimod) is a selective sphingosine 1 - phosphate receptor modulator that causes lymphocyte sequestration in the lymph nodes and presumably reduced migration to the central nervous system (Behrangi et al 2019). Mayzent is approved in the United States (US) for the

treatment of relapsing forms of multiple sclerosis (MS) including clinically isolated syndrome, relapsing remitting disease, and active secondary progressive disease in adults and in Canada for the treatment of patients with secondary progressive multiple sclerosis (SPMS) with active disease evidenced by relapses or imaging features characteristic of multiple sclerosis inflammatory activity, to delay the progression of physical disability.

Mayzent has been found to have a teratogenic and embryotoxic effect in studies in rats. Furthermore, the receptor family modulated by Mayzent (sphingosine 1 - phosphate receptor) is known to be involved in vascular formation during embryogenesis. Data on Mayzent exposure during pregnancy in the clinical program is very limited and it is not known whether Mayzent can affect pregnancy and infant outcomes in humans. Since it takes approximately 10 days to eliminate Mayzent from the body after stopping treatment, any drug administration on or after the 4th day post the first day of the last menstrual period (LMP) and up to the end of pregnancy may expose the fetus to the drug. This exposure period is derived by taking the conception date (operationalized here as first day of LMP+14 days) as the start of pregnancy and accounting for the above stated Mayzent elimination period (10 days). Based on the pathophysiological considerations and the potential for drug exposure during pregnancy, an evaluation of the effects of drug exposure immediately before and during pregnancy is warranted.

Reference is made to the approval letter for Mayzent dated March 26, 2019 and specifically the post-marketing requirement (PMR) 3591-4. The Mayzent Pregnancy Registry will be conducted to fulfill PMR 3591-4

The Pregnancy Exposure Registry is sponsored by Novartis and conducted by the Organization of Teratology Information Specialists (OTIS) Research Group. It is administered by investigators at the coordinating site located at the [REDACTED].

This is a United States (US) based registry designed to monitor pregnancy and infant outcomes among women in the US and Canada exposed to siponimod when used in accordance with the current approved prescribing informations in the US and Canada.

The goal of the Registry is to conduct an observational, prospective cohort study that will involve follow-up of live born infants to 1 year of age.

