## **Variables**

Exposure will be defined as siponimod treatment any time from the first day of the last menstrual period (LMP) prior to conception + 4 days up to and including the end of pregnancy by maternal report and verified by medical record review, with detailed information on the gestational timing, route of administration, dose, and dates of exposure. Outcome variables include major structural birth defects (including interventions for those defects and outcome up to one year of age), spontaneous abortion, stillbirth, elective termination, preterm delivery, minor structural defects, small for gestational age at birth, small for age on postnatal growth at 1 year of age, developmental performance on the Ages and Stages (ASQ) questionnaire for live born infants at 1 year of age, and serious or opportunistic infections in live born infants through the first year of life. Data will be obtained by maternal report, physical examination, and medical record review. Potential confounders or covariates to be collected include maternal age, race/ethnicity, socioeconomic status, body mass index (BMI), pregnancy and health history, lifestyle factors such as tobacco and alcohol use, comorbidities, medication, vaccine and vitamin/mineral exposures, and prenatal tests. Measures of disease severity will be collected for those enrolled in the siponimod-exposed and disease-matched cohorts. Details regarding definitions will be provided in the Statistical Analysis Plan (SAP) to be developed separately.

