### **Cohort 2: Disease-Matched Comparison Cohort (Comparison Group 1):**

1. Exposure to siponimod any time from the 4th day post the first day of LMP prior to conception up to and including end of pregnancy
2. Women with exposure to any of the following medications within 5 half-lives of conception:
  - Cladribine (Mavenclad)
  - SIP modulators
  - Teriflunomide (Aubagio)
  - Anti CD-20 monoclonal antibody

New medications (marketed after 2020) indicated for the treatment of MS will be evaluated for inclusion/exclusion criteria as the study progresses.

3. Women who have enrolled in the siponimod cohort or OMB157G2403 Kesimpta cohort with a previous pregnancy
4. Retrospective enrollment after the outcome of pregnancy is known (i.e. the pregnancy has ended prior to enrollment)
5. Results of a diagnostic test are positive for a major structural defect prior to enrollment. However, women who have had any normal or abnormal prenatal screening or diagnostic test prior to enrollment are eligible as long as the test result does not indicate a major structural defect.

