**Table 7-1 Variables**

Variable	Role	Data source(s)	Operational Definition
Exposure to siponimod	Exposure	Maternal report Medical record	Maternal report of exposure to siponimod of at least one dose any time from 4 th days post first day of LMP prior to conception up to and including the end of pregnancy. Confirmation of exposure with medical records.
Dose of siponimod	Exposure	Maternal report Medical record	Dose of siponimod mg per day (maternal report and confirmation with medical records).

Variable	Role	Data source(s)	Operational Definition
Duration of siponimod use	Exposure	Maternal report Medical record	Weeks of siponimod use in pregnancy (maternal report and confirmation with medical records).
Indication	Exposure	Maternal report Medical record	Indication for use of siponimod (maternal report and confirmation with medical records).
Gestational age at time of initial exposure to siponimod	Exposure	Maternal report Medical record	Gestational age at the time of initial exposure to siponimod (maternal report and confirmation with medical records).
Major structural birth defect	Outcome – primary	Maternal report Medical record OTIS investigator review Dysmorphology Evaluation	The Registry adopts the term “major structural defect” (i.e., birth defect) for an abnormality usually referred to as a “congenital abnormality” and defines major structural defect as follows:  Any major structural or chromosomal defect defined and classified, using the CDC Metropolitan Atlanta Congenital Defects Program (MACDP) classification of birth defects ( CDC 2017 ).(including any intervention to correct the structural defect and its outcome) in any pregnancy including those ending in a live born infant or a pregnancy loss.
Minor structural defect	Outcome - secondary	Dysmorphology Evaluation	A defect which occurs infrequently in the population but which has neither cosmetic nor functional significance to the child and is identified using a study related checklist incorporated into the study dysmorphology examination of live born infants.
Spontaneous abortion	Outcome - secondary	Maternal report Medical record	Non-deliberate embryonic or fetal death that occurs prior to 20.0 weeks’ gestation.

Variable	Role	Data source(s)	Operational Definition
Stillbirth	Outcome - secondary	Maternal report Medical record	A non-deliberate fetal death that occurs at or after 20.0 weeks' gestation but prior to delivery.

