Socioeconomic Category	Confounder	Maternal report	Hollingshead Socioeconomic Category based on maternal and paternal occupation and education (1-5).
Maternal Height	Confounder	Maternal report	Maternal height (cm).
Maternal Pre-pregnancy body weight	Confounder	Maternal report Medical record	Maternal pre-pregnancy body weight (kg) (confirm with medical record).
Maternal Pre-pregnancy BMI	Confounder	Maternal report	Maternal pre-pregnancy BMI (<18.5, 18.5-24.9, 25-29.9, >=30).
Number of times pregnant	Confounder	Maternal report Medical record	Number of times ever pregnant (1, 2-3, 4-5, >=6) (confirm with medical record).
Previous live birth or stillbirth deliveries	Confounder	Maternal report Medical record	Number of previous live birth or stillbirth deliveries (0, 1-2, 3-4, >=5) (confirm with medical record).

Variable	Role	Data source(s)	Operational Definition
Previous pregnancies ending in spontaneous abortion	Confounder	Maternal report Medical record	Number of previous pregnancies ending in spontaneous abortion (0, 1, 2, >=3) (confirm with medical record).
Previous pregnancies ending in elective termination	Confounder	Maternal report Medical record	Number of previous pregnancies ending in elective termination (0, 1, 2, >=3) (confirm with medical record).
Gestational age	Confounder	Maternal report Medical record	Weeks of pregnancy at time of enrollment, continuous and categorical (<13, 13-19.9, >=20): gestational age is calculated from the first date of LMP.
Referral source	Confounder	Maternal report	Source options: Sponsor, OTIS service, HCP, Internet, Other.
Geographic area of residence	Confounder	Maternal report	Geographic area of residence (e.g., US, Canada).
Disease Symptom/Severity measures	Confounder	Maternal report	Disease Symptom/Severity measures (exposed and disease-matched cohorts only).
Prenatal, Multivitamin, or Folic acid	Confounder	Maternal report	Prenatal, Multivitamin or Folic Acid supplement use by timing (began prior to conception, post-conception only, not taken at all).
Alcohol use in pregnancy	Confounder	Maternal report	Yes/No. Dose and frequency are captured.
Tobacco use in pregnancy	Confounder	Maternal report	Yes/No. Dose and frequency are captured.

Variable	Role	Data source(s)	Operational Definition

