#### **7.7.2.4 Outcome classification for secondary outcomes**

- ***Spontaneous abortion:*** spontaneous abortion/miscarriage is defined as non-deliberate fetal death which occurs prior to less than 20.0 weeks post-LMP.
- ***Analysis subset:*** the analysis subset for the secondary outcome of spontaneous abortion will be restricted in Cohort 1 to those who were exposed to any dose from

the 4th day post first day of LMP prior to conception to 20 weeks' gestation and enrolled prior to 20 weeks' gestation. The analysis subset for cohorts 2 and 3 will be restricted to those who enrolled prior to 20 weeks' gestation.

- **Stillbirth:** stillbirth is defined as non-deliberate fetal death anytime in gestation at or after 20 weeks post-LMP.
- **Elective termination:** elective termination/abortion is defined as deliberate termination of pregnancy at any time in gestation. Reasons for elective abortions are captured and are classified as due to medical reasons or social reasons.
- **Premature delivery:** premature delivery is defined as live birth prior to 37.0 weeks gestation as counted from LMP (or calculated from first-trimester ultrasound-derived due date if last menstrual period uncertain or more than 1 week discrepant). Elective caesarian deliveries or inductions prior to 37.0 completed weeks will be considered separately.
- **Preeclampsia / eclampsia:** preeclampsia or eclampsia reported by maternal interview with confirmation in medical record or report by medical record only is captured.
- **Small for gestational age:** small for gestational age is defined as birth size (weight, length or head circumference) less than or equal to the 10th centile for sex and gestational age using standard pediatric CDC growth curves for full term or preterm infants (CDC, 2000; Olsen et al., 2010).
- **Minor structural defects:** a minor structural defect is defined as a defect which has neither cosmetic nor functional significance to the child (e.g., complete 2,3 syndactyly of the toes). Minor structural defects will be identified only through the study dysmorphology examination for live born infants using the study-specific checklist.

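### Ultrasound-corrected dating applies to premature delivery only; the LMP+4 exposure window, trimester limits and gestational age stay on LMP, so a few women who stop near the cut-off can be misclassified

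*Protocol*

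**What the plan says.** The boundary is derived in the Abstract (Rationale and background) from two inputs: "Since it takes approximately 10 days to eliminate Mayzent from the body after stopping treatment", and "conception date (operationalized here as first day of LMP+14 days) as the start of pregnancy". The Abstract's Variables section then states the window: "Exposure will be defined as siponimod treatment any time from the first day of the last menstrual period (LMP) prior to conception + 4 days". The same start point appears in Section 6, in Cohort 1 inclusion 3, in Table 7-1 and in the primary analysis subset (Sections 7.7.2.2 and 7.7.3.1.1). It also appears in the first Cohort 2 exclusion, which runs from the 4th "day post the first day of LMP prior to conception up to and including end of pregnancy". None of these places mentions ultrasound dating.

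For the gestational-age covariate, Table 7-1 says that "gestational age is calculated from the first date of LMP". The primary subset ends with the first trimester, and no other dating basis is given for that limit.

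Section 7.7.2.4 is the exception. For premature delivery, gestational age is counted from LMP "or calculated from first-trimester ultrasound-derived due date if last menstrual period uncertain or more than 1 week discrepant". Table 7-1 counts the same outcome from LMP without that provision.

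**The concern.** The protocol accepts that LMP can be wrong by more than a week, and corrects it for one secondary outcome. It does not apply the correction to the variable that defines the exposed group in the primary comparison. An error of 7 days is large against an elimination allowance of about 10 days that carries no margin.

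Two errors can follow. If conception was later than LMP+14, a woman who had cleared the drug beforehand can count as exposed. If it was earlier, a woman with drug still present at conception can count as unexposed. If the drug is harmful and dating error is unrelated to the outcome, both pull the risk ratio towards 1. In a safety registry that is the direction that hides harm. There is also a plain inconsistency: one woman's exposure and delivery can be dated by different rules, and two sections of the protocol date premature delivery differently.

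**Working it through.** **The plan's own figure.** Conception at LMP+14 (Abstract), minus 10 days' elimination (Abstract): 14 − 10 = 4. The window start of LMP+4 is reproduced exactly.

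**Who changes status.** If ultrasound moves the LMP by d days, the corrected window starts at LMP+4+d. Only women whose last dose lies between LMP+4 and LMP+4+d are reclassified. A woman who takes siponimod well past both points is exposed under either dating.

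**A worked case.** LMP is recalled correctly but ovulation is late, with conception at LMP+35 and the last dose at LMP+10.
- Written rule: 10 is later than 4, so she is exposed and enters the primary subset.
- Drug cleared by 10 + 10 = LMP+20, which is 35 − 20 = 15 days before conception.
- LMP implied by ultrasound: 35 − 14 = LMP+21. The discrepancy of 21 days exceeds 7, so the Section 7.7.2.4 rule would apply.
- Corrected window start: 21 + 4 = LMP+25. Her last dose precedes it, so she is unexposed on corrected dates.

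**What the correction leaves.** Discrepancies of up to 7 days do not trigger it. The true cut-off could still lie anywhere from 4 − 7 = LMP−3 to 4 + 7 = LMP+11.

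**How many women (assumed inputs, not in the documents).** Take last dose as uniform within 14 days either side of the cut-off, and dating error as normal with SD 3 to 10 days. Simulation then gives about 8% to 26% misclassified among women that close. If 5% to 40% of women are that close, the overall share runs from about 0.4% (0.05 × 0.085) to about 10% (0.40 × 0.259).

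**Effect on the risk ratio.** Inputs from Table 7-4: 3% in the comparison group, risk ratio 3.0 (so 9% when exposed), 231 per group. Let f be the share of Cohort 1 truly unexposed and g the share of Cohort 2 truly exposed; both are assumed. Observed risks are p1 = 0.09(1 − f) + 0.03f and p2 = 0.03(1 − g) + 0.09g.

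| f | g | p1 | p2 | Observed RR | Power (normal approximation) |
|---|---|---|---|---|---|
| 0 | 0 | 0.0900 | 0.0300 | 3.00 | 77.7% |
| 1% | 1% | 0.0894 | 0.0306 | 2.92 | 76.0% |
| 10% | 0 | 0.0840 | 0.0300 | 2.80 | 70.8% |
| 10% | 3% | 0.0840 | 0.0318 | 2.64 | 67.2% |

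The 77.7% in the first row differs from the 80% in Table 7-4 before any misclassification. That is a separate matter; only the fall down the column bears on this point.

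**The case against.** **The wording already refers to the LMP before conception.** This stands, and it defeats a tempting example. A reader might infer that a woman who takes an early-pregnancy bleed for a period passes the Cohort 2 exclusion. Suppose the bleed is at true LMP+28 and the last dose at true LMP+30. The bleed comes 28 − 14 = 14 days after conception, so it is not the LMP prior to conception. By the text she is exposed and excluded from Cohort 2. Likewise, if a later true period was missed, that period is the relevant LMP. Late or early ovulation after a correctly recalled LMP is not rescued in this way, because conception is itself set at LMP+14.

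**The rule is openly an approximation and is meant to capture possible exposure.** This is fair for late ovulation, where it errs towards counting a woman as exposed. In the primary comparison that still dilutes Cohort 1.

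**Medical records and the analysis plan may settle it.** Exposure is checked: "Confirmation of exposure with medical records". That can establish that the drug was taken and when, but the window is still anchored to LMP. Sections 7.3 and the Abstract leave further definitions to the analysis plan, which may say how LMP is established. The silence alone would be no finding. The point rests on a rule already fixed in the eligibility criteria and Table 7-1, and on its disagreement with Section 7.7.2.4.

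**Cohort 2 also excludes S1P modulators within 5 half-lives of conception.** Read literally this covers siponimod, but it too needs a conception date.

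**The effect is small and assumed.** This stands. Section 7.9 expects exposure in unintended pregnancies, where treatment may often run past the cut-off (an inference). Giving misplaced Cohort 2 women the full threefold risk probably overstates that component, since those just past the cut-off had only residual drug. Section 7.7.2.2 also has timing and duration of exposure considered in the analysis.

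**Conclusion.** The point holds in a limited form. The protocol contains two dating rules, applies the better one to a single secondary outcome, and dates that outcome differently in Table 7-1. The exposure window, trimester limits and gestational age are on LMP without correction, so women who stop siponimod between the two cut-offs can be misclassified in the primary analysis.

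A reader might infer that every woman with a wrong LMP lands in the wrong cohort. The documents do not support that: her last dose must also fall between the two cut-offs. Nor do they show how often this happens. With 1% misplaced in each cohort, a true risk ratio of 3.0 appears as 2.92; with 10% of Cohort 1 and 3% of Cohort 2, as 2.64. These figures assume the stated shares, error unrelated to outcome, and full risk in misplaced Cohort 2 women. The likely effect is modest, but it runs towards missing harm and is cheap to remove.

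**What to change.** 1. State once, and refer to it in Section 6, Section 7.2.2, Table 7-1, Section 7.7.2.2 and Section 7.7.3.1.1, that LMP for the exposure window, trimester limits and gestational age is determined by the Section 7.7.2.4 rule. Say which date stands when no first-trimester ultrasound is available.
2. Align the Table 7-1 entries for premature delivery and gestational age with Section 7.7.2.4.
3. Settle each woman's exposure status for analysis on corrected dates, by staff blind to outcome. State beforehand whether a woman whose status changes moves to another analysis cohort or leaves the comparison.
4. Add a sensitivity analysis of the primary outcome that excludes women whose last dose is near the boundary. A margin of 7 days either side would match the tolerance in Section 7.7.2.4.

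The cost is protocol wording and a derivation step. Dates of siponimod use, due dates and prenatal ultrasound information are already collected or used. The downside is that a few women change or leave their analysis cohort, with a small loss of numbers.
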